## Description and Derivation of Efficacy/Health Outcomes Measures and Endpoints

Measure	Description	Variable	Derivation / Comment	Imputation Approach if Missing Components
	
 
The severity of 6 specific symptoms of AD (redness, swelling, oozing/crusting, excoriation, skin thickening/lichenification, dryness) is assessed using the following scale: none (0), mild (1), moderate (2), or severe (3) (for a maximum of 18 total points, assigned as “B” in the overall SCORAD calculation).
 
Subjective assessment of itch and of sleeplessness is recorded for each symptom by the patient or relative on a VAS, where 0 is no itch (or sleeplessness) and 10 is the worst imaginable itch (or sleeplessness), with a maximum possible score of 20 (assigned as “C” in the overall SCORAD calculation).
 
	
 
Change from baseline in SCORAD score
 
Percent change from baseline in SCORAD score
 
	Change from baseline: observed SCORAD score – baseline SCORAD score % change from baseline: $100 \times \frac{\text{Observed score} - \text{Baseline}}{\text{Baseline}}$	Missing if baseline or observed value is missing.
		SCORAD75	% Improvement in SCORAD from baseline $\geq 75\%$ : % change from baseline $\leq -75$	Missing if baseline or observed value is missing.
		SCORAD90	% Improvement in SCORAD from baseline $\geq 90\%$ : % change from baseline $\leq -90$	Missing if baseline or observed value is missing.
Pruritus Numeric Rating Scale (NRS)	The Pruritus NRS is an 11-point scale used by patients to rate their worst itch severity over the past 24 hours with 0 indicating “No itch” and 10 indicating “Worst itch imaginable.” Assessments will be recorded daily by the patient using an electronic diary (eDiary).	Pruritus NRS prorated weekly mean score	The prorated weekly mean is based on previous 7 days. If the patient has at least one daily score, the weekly mean is the prorated average of daily scores within the given week. Single item; range 0-10 eDiary data are mapped to study visit per Appendix 1 .	Weekly mean score missing if the patient has no Pruritus-NRS responses within the week.

Description and Derivation of Efficacy/Health Outcomes Measures and Endpoints

Measure	Description	Variable	Derivation / Comment	Imputation Approach if Missing Components
		
 
Change from baseline in Pruritus NRS prorated weekly mean score
 
Percent change from baseline in Pruritus NRS prorated weekly mean score
 
	Change from baseline: Observed Pruritus prorated weekly mean score – baseline Pruritus weekly mean score % change from baseline: $100 \times \frac{\text{Observed score} - \text{Baseline}}{\text{Baseline}}$	Missing if baseline or observed value is missing.
		4-point Pruritus improvement in Pruritus NRS prorated weekly mean score	Change from baseline $\leq$ -4 in Pruritus NRS prorated weekly mean score	Missing if baseline is missing or observed value is missing.
Sleep-loss due to pruritus	Sleep-loss due to pruritus will be assessed by the patient. Patients rate their sleep based on a 5-point Likert scale [0 (not at all) to 4 (unable to sleep at all)]. Assessments will be recorded daily by the patient using an electronic diary.	Sleep-loss prorated weekly mean score	The prorated weekly mean is based on previous 7 days. If the patient has at least one daily score within the week, the weekly mean is the prorated average of daily scores within the given week. Single item; range 0 to 4.. eDiary data are mapped to study visit per Appendix 1 .	Weekly mean score missing if the patient has no Sleep-loss score within the week.
		Change from baseline in Sleep-loss prorated weekly mean score  Percent change from baseline in Sleep-loss prorated weekly mean score	Change from baseline: observed sleep loss prorated weekly mean score – baseline sleep loss weekly mean score % change from baseline: $100 \times \frac{\text{Observed score} - \text{Baseline}}{\text{Baseline}}$	Missing if baseline or observed value is missing.
		2-point improvement in Sleep-loss prorated weekly mean score	Change from baseline in Sleep-loss prorated weekly mean score $\leq$ -2	Missing if baseline is missing or observed value is missing.

Description and Derivation of Efficacy/Health Outcomes Measures and Endpoints

Measure	Description	Variable	Derivation / Comment	Imputation Approach if Missing Components
Patient-Oriented Eczema Measure (POEM)	The POEM is a 7-item, validated, questionnaire used by the patient to assess disease symptoms over the last week. The patient is asked to respond to 7 questions on skin dryness, itching, flaking, cracking, sleep loss, bleeding and weeping. All 7 answers carry equal weight with a total possible score from 0 to 28 (answers scored as: No days=0; 1–2 days = 1; 3-4 days = 2; 5–6 days = 3; everyday = 4). A high score is indicative of a poor quality of life. POEM responses will be captured using an electronic diary and transferred into the clinical database.	POEM score	POEM total score: sum of questions 1 to 7, Range 0 to 28.	If a single question is left unanswered, then that question is scored as 0. If more than one question is unanswered, then the tool is not scored. If more than one response is selected, then the response with the highest score is used.
		Change from baseline in POEM score	Change from baseline: observed POEM score – baseline POEM score	Missing if baseline or observed value is missing.
		4-point improvement	Change from baseline $\leq -4$	Missing if baseline is missing or observed value is missing.
Dermatology Life Quality Index (DLQI)	DLQI is a validated, dermatology-specific, patient-reported measure that evaluates patient’s health-related QoL. This questionnaire has 10 items that are grouped in 6 domains, including symptoms and feelings, daily activities, leisure, work and school, personal relationships, and treatment. The recall period of this scale is over the “last week”. Response categories and corresponding scores are: Very much = 3 A lot = 2 A little = 1 Not at all = 0 Not relevant = 0	DLQI total score	A DLQI total score is calculated by summing all 10 question responses and has a range of 0-30 (less to more impairment) (Finlay and Khan 1994; Basra et al. 2008).	Score of 1 unanswered question = 0; If 2 or more questions are missing, the total score is missing. Note: #7B could be a valid missing while #7A is not “No.” That is, #7 should be considered as 1 question.
		DLQI (0,1)	A DLQI (0,1) response is defined as a postbaseline DLQI total score of 0 or 1. A DLQI total score of 0 to 1 is considered as having no effect on a patient’s HRQoL (Khilji et al. 2002; Hongbo et al. 2005).	Missing if DLQI total score is missing
		4-point improvement	Change from baseline $\leq -4$	Missing if baseline is missing or observed value is missing.
		DLQI total score and domain scores change from baseline	Calculated as: observed DLQI (total score or domain scores) – baseline DLQI (total score or domain scores)	Missing if baseline or observed value is missing

Description and Derivation of Efficacy/Health Outcomes Measures and Endpoints

Measure	Description	Variable	Derivation / Comment	Imputation Approach if Missing Components
	Scores range from 0-30 with higher scores indicating greater impairment of quality of life. A DLQI total score of 0 to 1 is considered as having no effect on a patient’s health-related QoL (Hongbo et al. 2005), and a 4-point change from baseline is considered as the minimal clinically important difference threshold (Khilji et al. 2002; Basra et al. 2015)	DLQI symptoms and feelings domain	Sum of responses of questions #1 and #2: #1. How itchy, sore, painful or stinging has your skin been? #2. How embarrassed or self-conscious have you been because of your skin?	If 1 question in a domain is missing, that domain is missing.
		DLQI daily activities domain	Sum of responses of questions #3 and #4: #3. How much has your skin interfered with you going shopping or looking after your home or garden? #4. How much has your skin influenced the clothes you wear?	If 1 question in a domain is missing, that domain is missing.
		DLQI leisure domain	Sum of responses of questions #5 and #6: #5. How much has your skin affected any social or leisure activities? #6. How much has your skin make it difficult for you to do any sport?	If 1 question in a domain is missing, that domain is missing.
		DLQI work and school domain	Sum of responses of questions question #7A and #7B: #7A. Has your skin prevented you from working or studying? #7B. If No: how much has your skin been a problem at work or studying?	If the answer to question #7A is missing, this domain is missing. If #7A is No, and #7B is missing, this domain is missing.

Description and Derivation of Efficacy/Health Outcomes Measures and Endpoints

Measure	Description	Variable	Derivation / Comment	Imputation Approach if Missing Components
		DLQI personal relationships domain	Sum of responses of questions #8 and #9: #8. How much has your skin created problems with your partner or any of your close friends or relatives? #9. How much has your skin caused any sexual difficulties?	If 1 question in a domain is missing, that domain is missing.
		DLQI treatment domain	Response of question #10: #10. How much of a problem has the treatment for your skin been, for example by making your home messy, or by taking up time?	If 1 question in a domain is missing, that domain is missing.
Children’s Dermatology Life Quality Index (CDLQI)	
The CDLQI is designed to measure the impact of any skin disease on the lives of children. Patients ≤16 years will complete the CDLQI and should continue to complete the CDLQI for the duration of the study.
 
The scoring of each question is:
 
 
• Very much = 3
 
• Quite a lot = 2
 
• Only a little = 1
 
• Not at all = 0
 
• Question unanswered = 0
 
• Question 7: 'Prevented school' (text-only questionnaire) = 3
 
	CDLQI total score	A CDLQI total score is calculated by summing all 10 question responses and has a range of 0-30 (less to more impairment) (Waters et al. 2010).	Score of 1 unanswered question = 0; If 2 or more questions are missing, the total score is missing.
		CDLQI (0,1)	A CDLQI (0,1) response is defined as a postbaseline CDLQI total score of 0 or 1.	Missing if CDLQI total score is missing
		4-point improvement	Change from baseline ≤-4	Missing if baseline is missing or observed value is missing.
		CDLQI total score and domain scores change from baseline	Calculated as: observed CDLQI (total score or domain scores) – baseline CDLQI (total score or domain scores)	Missing if baseline or observed value is missing

Description and Derivation of Efficacy/Health Outcomes Measures and Endpoints

Measure	Description	Variable	Derivation / Comment	Imputation Approach if Missing Components
		CDLQI symptoms and feelings domain	Sum of responses of questions #1 and #2: #1. Over the last week, how itchy, “scratchy”, sore, or painful has your skin been? #2. Over the last week, how embarrassed or self-conscious , upset , or sad have you been because of your skin?	If 1 question in a domain is missing, that domain is missing.
		CDLQI sleep	Responses of questions 9 #9. Over the last week, how much has your sleep been affected by your skin problem?	Single item, missing if missing.
		CDLQI leisure domain	Sum of responses of questions #4, #5 and #6: #4. Over the last week, how much have you changed or worn different or special clothes/shoes because of your skin? #5. Over the last week, how much has your skin trouble affected going out, playing, or doing hobbies ? #6. Over the last week, how much have you avoided swimming or other sports because of your skin trouble?	If 1 question in a domain is missing, that domain is missing.
		CDLQI school or holiday domain	Responses of questions 7: If select ‘Prevented school,’ score = 3  
 
 
Last week, was it school time?
 
OR
 
was it holiday time?
 
 
 
 
 
If school time: Over the last week, how much did your skin problem affect your school work?
 
If holiday time: How much over the last week, has your skin problem interfered with your enjoyment of the holiday?
 
 
	Single item, missing if missing.

Description and Derivation of Efficacy/Health Outcomes Measures and Endpoints

Measure	Description	Variable	Derivation / Comment	Imputation Approach if Missing Components
		CDLQI personal relationships domain	Sum of responses of questions #3 and #8: #3: Over the last week, how much has your skin affected your friendships ? #8. Over the last week, how much trouble have you had because of your skin with other people calling you names, teasing, bullying, asking questions or avoiding you?	If 1 question in a domain is missing, that domain is missing.
		CDLQI treatment domain	Response of question #10: #10. How much of a problem has the treatment for your skin been?	Single item, missing if missing.
European Quality of Life–5 Dimensions–5 Levels (EQ-5D-5L)	EQ-5D comprises five dimensions: mobility, self-care, usual activities, pain/discomfort and anxiety/depression. The EQ VAS records the patient’s self-rated health on a vertical visual analogue scale. The scores on these five dimensions can be presented as a health profile or can be converted to a single summary index number (utility) reflecting preferability compared to other health profiles	EQ-5D mobility EQ-5D self-care EQ-5D usual activities EQ-5D pain/discomfort EQ-5D anxiety/depression	Five health profile dimensions, each dimension has 5 levels: 1 = no problems 2 = slight problems 3 = moderate problems 4 = severe problems 5 = extreme problems. It should be noted that the numerals 1 to 5 have no arithmetic properties and should not be used as a primary score.	Each dimension is a single item, missing if missing.
		EQ-5D VAS	Single item. Range 0 to 100. 0 represents “worst health you can imagine” 100 represents “best health you can imagine”	Single item, missing if missing.
		Change from baseline in EQ-5D VAS	Change from baseline: observed EQ-5D VAS score – baseline EQ-5D VAS score	Missing if baseline or observed value is missing.
		EQ-5D-5L UK Population-based index score (health state index)	Derive EQ-5D-5L UK Population-based index score according to the link by using the UK algorithm to produce a patient-level index score between -0.59 and 1.0 (continuous variable).	N/A – partial assessments cannot be saved on the eCOA tablet.

Description and Derivation of Efficacy/Health Outcomes Measures and Endpoints

Measure	Description	Variable	Derivation / Comment	Imputation Approach if Missing Components
		Change from baseline in EQ-5D-5L UK Population-based index score	Change from baseline: observed EQ-5D-5L UK score – baseline EQ-5D-5L UK score	Missing if baseline or observed value is missing.
		EQ-5D-5L US Population-based index score (health state index)	Derive EQ-5D-5L US Population-based index score according to the link by using the US algorithm to produce a patient-level index score between -0.11 and 1.0 (continuous variable).	N/A – partial assessments cannot be saved on the eCOA tablet.
		Change from baseline in EQ-5D-5L US Population-based index score	Change from baseline: observed EQ-5D-5L US score – baseline EQ-5D-5L US score	Missing if baseline or observed value is missing.
Patient-Reported Outcomes Measurement Information System (PROMIS®)	PROMIS® is a set of person-centered measures that evaluates and monitors physical, mental, and social health in adults and children. Pediatric and tools for anxiety and depression. Patients ≤17 years will complete pediatric versions for the duration of the study.	PROMIS anxiety total score PROMIS depression total score	A PROMIS anxiety has 8 questions on Emotion Distress-Anxiety (or Pediatric Anxiety) -Short Form 8a. Each ranges 1 to 5. Total raw scores are converted to T-Scores with higher scores representing greater anxiety.  A PROMIS depression has 8 questions on Emotion Distress-Depression (or Pediatric Depressive Symptom) -Short Form 8a. Each ranges 1 to 5. Total raw scores are converted to T-score with higher scores representing greater depression.. Calculation is made by HealthMeasures Scoring Service, powered by Assessment Center SM	Total score can be derived even with partial response as instrument use item response theory method.

Description and Derivation of Efficacy/Health Outcomes Measures and Endpoints

Measure	Description	Variable	Derivation / Comment	Imputation Approach if Missing Components
		Change from baseline in PROMIS anxiety total score Change from baseline in PROMIS depression total score	Change from baseline: observed score – baseline PROMIS anxiety total score Change from baseline: observed score – baseline PROMIS depression total score	Missing if baseline or observed value is missing.
Asthma Control Questionnaire (ACQ-5)	Patients who report comorbid asthma prior to enrollment will complete the Asthma Control Questionnaire in addition to other patient reported outcomes in this trial. The ACQ-5 has been shown to reliably measure asthma control and distinguish patients with well-controlled asthma (score $\leq 0.75$ points) from those with uncontrolled asthma (score $\geq 1.5$ points). It consists of 5 questions that are scored on a 7-point Likert scale with a recall period of 1 week. The total ACQ-5 score is the mean score of all questions; a lower score represents better asthma control.	ACQ-5 total score	An ACQ-5 total score is the mean score of all 5 questions.	If more than 1 question is missing, the ACQ-5 total score is missing.
		Change from baseline in ACQ-5 score	Change from baseline: observed ACQ-5 total score – baseline ACQ-5 total score	Missing if baseline or observed value is missing.
		MCID of 0.5	Change from baseline $\leq -0.5$	Missing if baseline is missing or observed value is missing.

**Description and Derivation of Efficacy/Health Outcomes Measures and Endpoints**

Measure	Description	Variable	Derivation / Comment	Imputation Approach if Missing Components
Topical corticosteroid (TCS) or topical calcineurin inhibitor (TCI) Use	A mid-potency TCS, triamcinolone acetonide 0.1% cream, and a low-potency TCS, hydrocortisone 1% cream (for use on sensitive skin areas) will be provided by the Sponsor or clinical site for use in this trial. Patients are to be instructed to return all used and unused TCS medication (tubes) to the study site for accountability purposes. All TCS and TCI use will be recorded daily by the patient using an electronic diary	Time (days) to TCS / TCI-free use from Baseline to Week 16	Days from first study drug injection to the day patient stop using all TCS/TCI (if a patient start and stop using low or mid-potency TCS/TCI multiple times, use the last stop date as the stop date for this patient )	If do not stop using the TCS/TCI, the patient will be censored at the date of their last visit
		Proportion of TCS/TCI free days from Baseline to Week 16	Number of the total TCS/TCI free days divided by total number of days during the treatment period	Missing data will be treated as TCS/TCI used days.
Modified Subcutaneous Administration Assessment Questionnaire (SQAAQ)	Adolescent patients from EU may complete the modified SQAAQ which uses 10 questions to assess the acceptability and tolerability with using a device to administer a subcutaneous injection. The person who administered the dose (adolescent patient or their parent/caregiver) should complete a 7-point Likert scale (from “Strongly Disagree” to “Strongly Agree”) shortly after completing the injection.	Respond “Strongly Agree” or “Agree” for each self/caregiver administration of the study drug.	For each EU adolescent patient that have SQAAQ scale completed, the proportion of patients who answer “Strongly Agree” or “Agree” in each of the 10 questions.	Missing data will be treated as missing.

Abbreviations: AD = atopic dermatitis; MCID = minimally clinically important difference; QoL = quality of life; VAS = Visual Analog Scale.

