## 6.2. Primary and Supportive Estimands

There will be 3 estimands of interest in analyzing primary and major secondary endpoints for the Double-Blinded Treatment Period. Two types of intercurrent events (ICEs) in terms of estimating the treatment effects for the treatment period will be considered: Initiation of rescue medication as defined in [Appendix 2](#) and permanent treatment discontinuation.

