### 6.2.1. Primary Estimand (Hybrid)

The primary estimand is a hybrid estimand representing the primary clinical question of interest: What is the difference between treatment conditions (that is, lebrikizumab vs placebo) in the target patient population in successful responses or means after 16 weeks achieved without use of rescue medication, and if all patients continued with treatment except those who discontinued due to lack of efficacy?

The primary estimand is described by the following attributes:

- Population: Defined through appropriate inclusion/exclusion criteria to reflect the targeted patient population for approval
- Endpoint: Apply to all primary and major secondary endpoints
- How to account for ICEs
  - Subjects who require any use of rescue medication or discontinued treatment due to lack of efficacy prior to Week 16 will be considered as treatment failures, that is, nonresponder, after the ICEs. Therefore, composite strategy is used for these types of ICEs.
  - For subjects who discontinue treatment due to reasons other than lack of efficacy prior to Week 16, a hypothetical strategy will be used to estimate what the treatment effect would have been if subjects continued with treatment. Therefore, hypothetical strategy is used for these types of ICEs.
- Population-level summary: Difference in response proportions or means between treatment conditions.

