### 6.4.3. Nonresponder Imputation

The nonresponder imputation (NRI) method will be used to handle missing data relative to the supportive estimand for categorical endpoints (composite). Patients who receive rescue medication (high potency TCS or systemic AD treatment, defined in [Appendix 2](#)), or discontinue treatment, will be set to non-response subsequent to this time through Week 16. Intermittent missing values will also be set to non-response.

The NRI method imputes missing values as non-responders and can be justified based on the composite strategy (ICH E9R1) for handling ICEs. In this strategy patients are defined as responders only if they meet the clinical requirements for response at the predefined time AND they remain on the assigned study treatment (that is, not using rescue medications and not having missing values due to other reasons). Failing either criteria by definition makes them nonresponders.

Randomized patients without at least 1 postbaseline observation will also be defined as nonresponders for all visits for the NRI analysis.

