#### **6.4.5. Mixed-effects Model for Repeated Measures (MMRM)**

Mixed-model for repeated measures analyses will be performed on continuous endpoints to mitigate the impact of missing data. This approach assumes missing observations are missing-at-random (missingness is related to observed data) and borrows information from patients in the same treatment arm taking into account both the missingness of data through the correlation of the repeated measurements.

The values subsequent to rescue medication use (high-potency TCS or systemic AD treatment, defined in [Appendix 2](#)) or treatment discontinuation will be made missing before applying the MMRM. The MMRM is described in Section [6.1.2](#).

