	Change from baseline in 
 
• EQ-5D VAS
 
• EQ-5D-5L UK Population-based index score
 
• EQ-5D-5L US Population-based index score
 
	ANCOVA with LOCF	mITT	Leb 250 mg Q2W vs PBO; Week 16	Secondary analysis
Patient-Reported Outcomes Measurement Information System (PROMIS®)	Change from baseline in PROMIS Anxiety score  Change from baseline in PROMIS Depression score	ANCOVA with LOCF	mITT	Leb 250 mg Q2W vs PBO; Week 16	Secondary analysis
Asthma Control Questionnaire (ACQ-5)	Change from baseline in ACQ-5 score	ANCOVA with LOCF	mITT with self-reported comorbid asthma	Leb 250 mg Q2W vs PBO; Week 16	Secondary analysis
Topical corticosteroid (TCS) or topical calcineurin inhibitor (TCI) Use	Time (days) to TCS / TCI-free use from Baseline to Week 16	KM method with log-rank test	mITT	Leb 250 mg Q2W vs PBO;	Secondary analysis
	Proportion of TCS/TCI free days from Baseline to Week 16	MMRM	mITT	Leb 250 mg Q2W vs PBO; Week 16 and all scheduled visits	Secondary analysis

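### Time to TCS/TCI-free use has no rule for rescue or lack-of-efficacy discontinuation, so a recorded last stop counts as a TCS-free event regardless (minor)

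*SAP*

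**What the plan says.** SAP Table KGAD.6.8 (row on TCS or TCI use) measures days from first injection to the day the patient stops all TCS/TCI. For patients who "start and stop using low or mid-potency TCS/TCI multiple times", the rule is to "use the last stop date as the stop date for this patient". The one censoring rule is for a patient who does not stop: "the patient will be censored at the date of their last visit". Table KGAD.6.9 gives the analysis as "KM method with log-rank test" in the mITT Population. SAP 6.1.2 adds that the log-rank test is stratified. None of these places mentions rescue or discontinuation.

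Elsewhere the SAP does deal with both:

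- SAP 6.2 sets the scope: "There will be 3 estimands of interest in analyzing primary and major secondary endpoints".
- SAP 6.2.1 (primary estimand): "Subjects who require any use of rescue medication or discontinued treatment due to lack of efficacy prior to Week 16 will be considered" treatment failures.
- SAP 6.4.3 (NRI): patients with rescue or any treatment discontinuation "will be set to non-response subsequent to this time through Week 16".
- SAP 6.4.4 (LOCF) and 6.4.5 (MMRM): values after rescue are dropped; in 6.4.5, values after rescue "or treatment discontinuation will be made missing before applying the MMRM".

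Table KGAD.6.5, which assigns these methods, has categorical and continuous rows but no time-to-event row.

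Protocol Table 1 lists the endpoint as secondary for both FDA and EMA. SAP Table KGAD.4.1 places it among the other efficacy endpoints, and it is in neither testing list in SAP 6.6.

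**The concern.** Systemic rescue is not TCS or TCI, so it cannot undo a recorded stop. Under Protocol 6.4, patients given systemic rescue come off study drug but continue to attend visits. Under Protocol Section 3, TCS may be tapered or stopped according to response. A patient could therefore clear on systemic rescue, stop the cream, and enter the Kaplan-Meier curve as a TCS-free event for the randomised arm. A patient who stops the cream and then discontinues for lack of efficacy is also kept as an event.

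At stake is the between-arm comparison on this one endpoint. It matters somewhat in a TCS-combination trial, because it bears on whether the drug spares topical treatment, and SAP 6.1 plans to report the Protocol Table 1 endpoints in the study report.

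**Working it through.** **1. Is there a stated figure?** Not for this endpoint. The plan's only power statement (above 95%, SAP 5.2) concerns IGA 0/1 and EASI-75. At 150:75 with a two-sided Fisher test it reproduces: 98.4% for 38% vs 13%, and above 99.9% for 58% vs 20%. It has no bearing on this point.

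**2. Apply the rule literally.** Event = last stop date; censor only if the patient does not stop. Day 112 is 16 × 7.

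| Patient | As written | Rescue or lack of efficacy as non-event |
|---|---|---|
| Stops Day 40, systemic rescue Day 50 | event, Day 40 | non-event to Day 112 |
| Stops Day 40, discontinues for lack of efficacy Day 57 | event, Day 40 | non-event to Day 112 |
| Stops Days 20 and 70, neither occurs | event, Day 70 | event, Day 70 |

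**3. Compare with the SAP's other rules.** The composite rules (6.2.1, 6.2.2, 6.4.3) make the first two patients failures. The hypothetical rules (6.2.3, 6.4.4, 6.4.5) drop data after rescue or discontinuation. None of them would credit a stop that follows rescue. A stop recorded before rescue is cancelled only by the composite rules.

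**4. Size, on assumed rates.** Let f be the share of an arm with rescue or lack-of-efficacy discontinuation, and c the share of those with a recorded last stop. Each arm's event rate rises by c × f, so the difference shifts by c × (f lebrikizumab − f placebo). With f differing by 10 points:

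- c = 10%: 1 point
- c = 20%: 2 points
- c = 40%: 4 points

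Patients affected at c = 20%:

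- f 5% vs 15%: 150 × 0.05 × 0.2 = 1.5 on lebrikizumab and 75 × 0.15 × 0.2 = 2.25 on placebo.
- f 15% vs 5%: 150 × 0.15 × 0.2 = 4.5 and 75 × 0.05 × 0.2 = 0.75.

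Put another way, if 40% of each arm has a recorded stop, and 5% of those stoppers on lebrikizumab and 20% on placebo are such patients, the shift is 40% × (20% − 5%) = 6 points.

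**5. Effect on the test, simulated.** Assumptions: 150:75, unstratified log-rank, two-sided 0.05, 112 days, 6,000 trials per setting, true TCS-free rates 40% vs 20%, failures split evenly between rescue and lack-of-efficacy leavers. With these patients as non-events to Day 112, power is 0.85 to 0.87. As written:

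| f, lebrikizumab vs placebo | c = 10% | c = 20% | c = 40% |
|---|---|---|---|
| 5% vs 15% | 0.78 | 0.74 | 0.60 |
| 10% vs 10% | 0.85 | 0.85 | 0.83 |
| 15% vs 5% | 0.91 | 0.93 | 0.95 |

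About 0.03 of the change in the unequal rows comes from censoring lack-of-efficacy leavers at their last visit: at c = 0 power is 0.84 and 0.90, against 0.87. With f differing by only 3 points (2% vs 5%, or 5% vs 8%), power falls from 0.86 to 0.82–0.84 at c = 10–20%.

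With equal true rates (30% in each arm), claims for lebrikizumab (nominal 2.5%) across the three values of c are 4.1%, 5.6% and 9.3% for f 15% vs 5%; about 2.5% for equal f; and 1.1%, 1.0% and 0.3% for f 5% vs 15%.

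**6. The patient who resumes.** Protocol 6.3 lets patients resume TCS at their discretion. One who stops, resumes and never stops again has a last stop date (event) but also has not stopped (censored). If use spells average 7 days and free spells 7, 14 or 28 days, the share using at Day 112 is about 7/14 = 50%, 7/21 = 33% or 7/35 = 20%. These spell lengths are assumed, and the model has no permanent stoppers, so it overstates the share whose status hangs on the reading.

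**The case against.** The strongest reply is that no SAP rule is broken. The estimands are limited to primary and major secondary endpoints, and this is neither. The endpoint measures when topical use ended, and counting that date whatever happens with systemic therapy is a legitimate treatment-policy choice. Nor do the documents single out the composite rule of 6.2.1: for remaining endpoints Table KGAD.6.5 uses NRI, under which every discontinuation fails, or a hypothetical approach. All of this stands, and it makes the point an omission. What remains is that the SAP never states a treatment-policy strategy here, and every rescue rule it does state points the other way.

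Three further limits stand:

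- A reader might infer that high-potency TCS escapes the definition because the repeat-stop clause names only low or mid potency. Appendix 2 places high-potency products (D07AC, D07AD) within TCS (D07), so stopping all TCS/TCI already covers them.
- A reader might contrast this endpoint with the proportion of TCS/TCI-free days, which is analysed by MMRM. That contrast is not clean: Table KGAD.6.8 counts missing days there as days of use, which must itself be squared with the set-to-missing rule in 6.4.5.
- The 9.3% needs failures to be three times as common on lebrikizumab, against the benefit the plan assumes, and those claims are false only if the composite target is accepted.

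**Conclusion.** The point holds as a minor gap. The rule as written counts a patient with a recorded last stop as TCS-free even if that patient is rescued systemically or discontinues for lack of efficacy before Week 16, and nothing else in the SAP overrides it for a Kaplan-Meier endpoint. This rests on literal application of the rule and on the SAP's silence; no sentence says that rescued patients are kept as events.

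Size and direction are not knowable from the documents, which give no rescue, discontinuation or stop rates. If such patients are commoner on placebo, the comparison loses power; if commoner on lebrikizumab, it flatters the drug; if equally common, the effect is small.

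A reader might infer that the SAP contradicts its own estimand, that the bias favours lebrikizumab, or that the main efficacy claim is at risk. The documents support none of these: SAP 6.2 limits the estimands, the direction is open, and the endpoint is outside both multiplicity-controlled lists, so primary and major secondary conclusions are unaffected.

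**What to change.** In Table KGAD.6.8:

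1. Count patients who use rescue medication (Appendix 2) or discontinue treatment for lack of efficacy before Week 16 as not achieving TCS/TCI-free use, and keep them in the risk set as non-events to Day 112.
2. State that a patient who resumes TCS/TCI and does not stop again is censored under the existing rule for patients who do not stop.
3. State that the end of diary entries is not a stop date.
4. Align the low or mid-potency parenthesis with the all-TCS/TCI wording.

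Handling of patients who leave for other reasons after a recorded stop can remain the sponsor's choice, but should be stated.

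SAP Section 3 records that the primary database lock has occurred. Statisticians blinded to the data should therefore make the change, or it should be reported as a labelled sensitivity analysis beside the rule as written. The cost is a few sentences and some derivation code, with no new data. The downside is fewer events and a little more derivation work.
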